LY3074828 (mirikizumab) is a humanized immunoglobulin G4 (IgG4)–variant monoclonal antibody that binds to the p19 subunit of IL-23 and does not bind IL-12. Mirikizumab is being developed for the treatment of immune-mediated or inflammatory diseases in which the IL-23 pathway is thought to have a pathogenic role. Study I6T-MC-AMAH (AMAH) is a confirmatory study testing mirikizumab as a treatment for plaque psoriasis and is intended to support registration of this indication. This Phase 3 trial is designed to contribute to the evaluation of the safety, and to evaluate the long-term efficacy as measured by improvement in disease severity and key patient-reported outcomes following long-term treatment with mirikizumab.

Objective(s)/Endpoints:

Objectives	Endpoints

Primary
 
 To evaluate the long-term maintenance of efficacy of mirikizumab in patients with moderate-to-severe plaque psoriasis 	
Over the duration of the study:
 
 Proportion of patients with an sPGA (0,1) among those who entered Study AMAH with sPGA (0,1) Proportion of patients who maintained a $\geq 90\%$ improvement in PASI (PASI 90) among those who entered Study AMAH with a PASI 90 response

Abbreviations: PASI = Psoriasis Area and Severity Index; PASI 90 = $\geq 90\%$ improvement in PASI from baseline; sPGA = static Physician's Global Assessment

Summary of Study Design:

Study AMAH is a long-term study in which patients completing one of four originator studies (16T-MC-AMAF [AMAF], 16T-MC-AMAJ [AMAJ], 16T-MC-AMAK [AMAK], or 16T-MC-AMBK [AMBK]) will receive mirikizumab for an extended period of time (approximately 4 years or until commercial availability of mirikizumab), and then enter a 12-week Post-Treatment Follow-Up period (Figure AMAH.1). Patients who qualify for Study AMAH may enter directly into the study upon the final visit of a qualifying study period of the originator study. The qualifying study periods of the originator studies are as follows:

- AMAJ, AMAK, AMAF: Blinded Maintenance Period
- AMBK: Treatment Period

Most patients will enter Study AMAH at the last visit of a qualifying study period of the originator studies. All patients must enter Study AMAH within 12 weeks of their final visit in these periods or they will become ineligible. Patients in the secukinumab treatment group of Study AMAJ will be eligible to enter Study AMAH; such patients will receive mirikizumab for the first time in Study AMAH.

Treatment Period:

All patients participating in Study AMAH will receive subcutaneous (SC) administration of mirikizumab every 8 weeks (Q8W). The dose used in Study AMAH will depend on the treatment that the patients were receiving during the qualifying period of the originator study. For all treatment groups in Study AMAH, dosing begins at Visit 1 and continues to Week 208.

- Patients entering from Study AMAJ or Study AMAK who received mirikizumab during the qualifying period will continue to receive the dose they were receiving (either 250 mg mirikizumab Q8W SC or 125 mg mirikizumab Q8W SC). Patients entering from Study AMAJ or Study AMAK who were receiving secukinumab or placebo, respectively, during the qualifying period will receive 250 mg mirikizumab Q8W SC.
- Patients entering from Study AMBK will receive 250 mg mirikizumab Q8W SC.
- Patients entering from Study AMAF whose last treatment was 300 mg mirikizumab, on either the fixed Q8W dosing regimen or on the as-needed (PRN) regimen, will start 250 mg mirikizumab Q8W SC in Study AMAH. Patients entering from Study AMAF whose last treatment was either 30 mg or 100 mg mirikizumab on a PRN regimen will start 125 mg mirikizumab Q8W SC in Study AMAH.
- After Study AMAH dosing is no longer blinded, patients who in the opinion of the investigator have experienced significant clinically meaningful loss of efficacy during study participation may be increased from 125 mg mirikizumab Q8W to 250 mg mirikizumab Q8W if it is determined by the patient and the investigator that the patient might benefit from additional study drug in order to maintain satisfactory disease

control. All patients who increase dosing to 250 mg mirikizumab Q8W will remain on this dose until completion of the study or early discontinuation.

Post-Treatment Follow-up Period (12 weeks):

All patients, whether they discontinue early for any reason or else complete study treatment, will enter the 12-week Post-Treatment Follow-Up Period.

Number of Patients:

Approximately 1600-2000 participants are expected to enroll in Study AMAH from the originator studies.

Statistical Analysis:

The sample size for Study AMAH will be determined by the number of patients who continue into Study AMAH from the originator studies.

The analysis will be focused on point estimates and confidence intervals. Thus, no hypothesis testing will be performed, and multiple testing will not need to be accounted for.

Efficacy and safety summaries will be reported by the following 3 cohorts:

- (1) Patients assigned to 250 mg mirikizumab Q8W SC in Study AMAH, excluding patients who received secukinumab during the qualifying period of their originating study.
- (2) Patients assigned to 125 mg mirikizumab Q8W SC in Study AMAH
- (3) Patients who received secukinumab during the qualifying period of their originating study.

For assessment of the primary endpoints and other categorical efficacy endpoints, proportions and 95% confidence intervals will be reported using the simple asymptotic method, without continuity correction (that is, normal approximation to the binomial distribution). For the primary endpoint, missing data will be handled in at least 2 different ways: (1) proportions, calculated using only observed data, and (2) non-responder imputation (NRI). For the NRI method, all patients who do not meet the clinical response criteria or have missing clinical response data at the analysis time point will be defined as nonresponders.

For continuous efficacy and health outcome variables with multiple post-baseline measurements, the mean response over time will be estimated using the mixed-effects model for repeated measures (MMRM). For continuous efficacy and health outcome variables with a single post-baseline time point, the mean response will be estimated using analysis of covariance (ANCOVA).

Continuous safety data, including vital sign and laboratory values, will be analyzed by ANCOVA with treatment and baseline value in the model, unless otherwise specified. Also,

laboratory analytes will be presented as mean changes from baseline and as incidence of shift between normal and abnormal states.

A single Data Monitoring Committee consisting of members external to Eli Lilly and Company will be established for interim safety monitoring across all Phase 3 trials in patients with psoriasis.

2. Schedule of Activities

Table AMAH.1. Schedule of Activities

Procedure ^a	Treatment Period (Visits 1-14, every-8-week visits)													
	V1 ^b	V2	V3	V4	V5	V6	V7	V8	V9	V10	V11	V12	V13	V14
Visit Number	0	8	16	24	32	40	48	56	64	72	80	88	96	104
Week Relative to Study Drug Initiation	0	8	16	24	32	40	48	56	64	72	80	88	96	104
Day Relative to Study Drug Initiation, with Visit Tolerance Interval	1 ± 5	57 ± 5	113 ± 5	169 ± 5	225 ± 5	281 ± 5	337 ± 5	393 ± 5	449 ± 5	505 ± 5	561 ± 5	617 ± 5	673 ± 5	729 ± 5
Informed consent	X													
Demographics	X													
Physical examination ^c	X													
Weight	X													
Review and confirm inclusion/exclusion criteria	X													
Complete medical/surgical history and habits	X													
Concomitant medications	X	X	X	X	X	X	X	X	X	X	X	X	X	X
Preexisting conditions	X													
Adverse events	X	X	X	X	X	X	X	X	X	X	X	X	X	X
Vital signs (BP, temperature, and heart rate) ^d	X	X	X	X	X	X	X	X	X	X	X	X	X	X
PPD/Quantiferon-TB Gold/T-SPOT.TB [®] (per local guidelines) ^e	TB testing required only based on clinical assessment of TB risk (symptoms/signs/known or suspected TB exposure), and according to local regulations and/or local standard of care.													
ECG ^f														
C-SSRS	X	X	X	X	X	X	X	X	X	X	X	X	X	X
Self-Harm Supplement Form ^g	X	X	X	X	X	X	X	X	X	X	X	X	X	X
Self-Harm Follow-up Form	X	X	X	X	X	X	X	X	X	X	X	X	X	X
QIDS-SR16 (patient completed)	X	X	X	X	X	X	X	X	X	X	X	X	X	X
IP dosed	X	X	X	X	X	X	X	X	X	X	X	X	X	
IP dispensed														X ^h

Procedure ^a	Treatment Period (Visits 1-14, every-8-week visits)													
	Visit Number	V1 ^b	V2	V3	V4	V5	V6	V7	V8	V9	V10	V11	V12	V13
Week Relative to Study Drug Initiation	0	8	16	24	32	40	48	56	64	72	80	88	96	104
Day Relative to Study Drug Initiation, with Visit Tolerance Interval	1 ± 5	57 ± 5	113 ± 5	169 ± 5	225 ± 5	281 ± 5	337 ± 5	393 ± 5	449 ± 5	505 ± 5	561 ± 5	617 ± 5	673 ± 5	729 ± 5
Investigator-Completed Clinical Efficacy Scales														
PASI	X	X	X	X	X	X	X	X	X	X	X	X	X	X
BSA	X	X	X	X	X	X	X	X	X	X	X	X	X	X
sPGA	X	X	X	X	X	X	X	X	X	X	X	X	X	X
PSSI ⁱ	X	X	X	X	X	X	X	X	X	X	X	X	X	X
NAPSI ⁱ	X	X	X	X	X	X	X	X	X	X	X	X	X	X
PPASI ⁱ	X	X	X	X	X	X	X	X	X	X	X	X	X	X
Patient-Completed Health Outcomes Scales^j														
PSS	X	X	X	X	X	X	X	X	X	X	X	X	X	X
DLQI	X	X	X	X	X	X	X	X	X	X	X	X	X	X
Laboratory Tests														
Hematology ^k	X	X	X	X	X	X	X	X	X	X	X	X	X	X
Clinical serum chemistry ^k	X	X	X	X	X	X	X	X	X	X	X	X	X	X
Urinalysis	X													
hsCRP	X	X	X	X	X	X	X	X	X	X	X	X	X	X
HBV DNA testing ^l		X		X		X		X		X		X		X
HCV RNA testing	X ^m	X ^m	X ^m	X ^m	X ^m	X ^m	X ^m	X ^m	X ^m	X ^m	X ^m	X ^m	X ^m	X ^m
Immunogenicity for mirikizumab ⁿ	X ^o	X	X	X			X			X			X	
Serum for mirikizumab concentrations (PK) ^p	X ^o	X	X	X			X			X			X	
Urine pregnancy test ^q (local; WCBP only)	X	X	X	X	X	X	X	X	X	X	X	X	X	X

Procedure ^a	Treatment Period (Visits 15-21, every-16-week visits)							ETV ^r	Follow-up Period (Visits 801 and 802)	
	Visit Number	V15	V16	V17	V18	V19	V20		V21	V801
Week Relative to Study Drug Initiation	120	136	152	168	184	200	208		LV +4W	LV +12W
Day Relative to Study Drug Initiation, with Visit Tolerance Interval	841 ± 5	953 ± 5	1065 ± 5	1177 ± 5	1289 ± 5	1401 ± 5	1457 ± 5		29 ± 5	85 ± 5
Physical examination ^c								X		X
Weight							X	X		
Concomitant medications	X	X	X	X	X	X	X	X	X	X
Adverse events	X	X	X	X	X	X	X	X	X	X
Vital signs (BP, temperature, and heart rate) ^d	X	X	X	X	X	X	X	X	X	X
PPD/Quantiferon-TB Gold/ T-SPOT.TB [®] (per local guidelines) ^e	TB testing required only based on clinical assessment of TB risk (symptoms/signs/known or suspected TB exposure), and according to local regulations and/or local standard of care.									
ECG ^f								X		X
C-SSRS	X	X	X	X	X	X	X	X	X	X
Self-Harm Supplement Form ^g	X	X	X	X	X	X	X	X	X	X
Self-Harm Follow-up Form	X	X	X	X	X	X	X	X	X	X
QIDS-SR16 (patient completed)	X	X	X	X	X	X	X	X		X
IP dispensed	X	X	X	X	X	X	X			
IP returned	X	X	X	X	X	X	X	X	X	
Investigator-Completed Clinical Efficacy Scales										
PASI	X	X	X	X	X	X	X	X	X	X
BSA	X	X	X	X	X	X	X	X	X	X
sPGA	X	X	X	X	X	X	X	X	X	X
PSSI ⁱ	X	X	X	X	X	X	X	X	X	X
NAPSI ⁱ	X	X	X	X	X	X	X	X	X	X

Procedure ^a	Treatment Period (Visits 15-21, every-16-week visits)							ETV ^r	Follow-up Period (Visits 801 and 802)	
	Visit Number	V15	V16	V17	V18	V19	V20		V21	V801
Week Relative to Study Drug Initiation	120	136	152	168	184	200	208		LV +4W	LV +12W
Day Relative to Study Drug Initiation, with Visit Tolerance Interval	841 ± 5	953 ± 5	1065 ± 5	1177 ± 5	1289 ± 5	1401 ± 5	1457 ± 5		29 ± 5	85 ± 5
PPASI ⁱ	X	X	X	X	X	X	X	X	X	X
Patient-Completed Health Outcomes Scales^j										
PSS	X	X	X	X	X	X	X	X		X
DLQI	X	X	X	X	X	X	X	X		X
Laboratory Tests										
Hematology ^k	X	X	X	X	X	X	X	X	X	X
Clinical Serum chemistry ^k	X	X	X	X	X	X	X	X	X	X
Urinalysis									X ^s	X
HsCRP	X	X	X	X	X	X	X	X	X	X
HBV DNA testing ^l	X	X	X	X	X	X	X	X	X	X
HCV RNA testing	X ^m	X ^m	X ^m	X ^m	X ^m	X ^m	X ^m	X ^m	X ^m	X ^m
Immunogenicity for mirikizumab ⁿ	X		X		X		X			X
Serum for mirikizumab concentrations (PK) ^p	X		X		X		X			X
Urine pregnancy test ^q (local; WCBP only)	X	X	X	X	X	X	X	X		X

Abbreviations: ALT = alanine aminotransferase; BP = blood pressure; BSA = body surface area; C-SSRS = Columbia–Suicide Severity Rating Scale; DLQI = Dermatology Life Quality Index; DNA = deoxyribonucleic acid; ECG = electrocardiogram; ETV = early termination visit; HBcAb+ = positive for hepatitis B core antibody; HBV = hepatitis B virus; HCV = hepatitis C virus; hsCRP = high-sensitivity C-reactive protein; IP = investigational product; LV = last study visit; LVTP = last visit of a qualifying study treatment period; NAPSI = Nail Psoriasis Severity Index; PASI = Psoriasis Area and Severity Index; PK = pharmacokinetic; PPASI = Palmoplantar Psoriasis Severity Index; PPD = purified protein derivative (skin test); PSS = Psoriasis Symptoms Scale; PSSI = Psoriasis Scalp Severity Index; QIDS-SR16 = 16-item Quick Inventory of Depressive Symptomatology; RNA = ribonucleic acid; sPGA = static Physician’s Global Assessment; TB = tuberculosis; ULN = upper limit of normal; V = visit; W = weeks; WCBP = women of child-bearing potential.

^a All activities should be completed prior to any study dose administration, unless otherwise stated.

- b For most patients, the final visit of the originating study will coincide with Visit 1 (Week 0) of Study AMAH. In these cases, any assessments/procedures (including laboratory tests) conducted during the patient's final visit in the originating study should not be repeated for Visit 1 (Week 0) of Study AMAH. In cases where entry into Study AMAH is delayed beyond the LVTP of the originating study, assessments/procedures (including laboratory tests) indicated for Visit 1 (Week 0) of Study AMAH that are not conducted during the patient's last visit of the originating study will be performed as indicated in the Schedule of Activities. Visit 1 procedures may be conducted over more than 1 day as long as all tasks are completed within the allowable visit tolerance (at least 3 days should be allowed for receipt of laboratory test results).
- c One complete physical examination (excluding pelvic or rectal examinations) to include heart, lungs, peripheral lymph nodes, and abdomen, and visual examination of all skin areas (including genitalia and breast areas) will be performed at Visit 1. All physical examinations throughout the study should include a symptom-directed evaluation as well as examination of heart, lungs, peripheral lymph nodes, and abdomen, and visual examination of all skin areas (including genitalia and breast areas) (see Section 9.4.5.1.) Physical examination does not need to be performed again if Visit 1 occurs on the same date as the last visit of the originator study and if physical examination was performed at the last visit of the originator study.
- d When multiple assessments are scheduled for the same time point, the preferred order of completion should be as follows: vital signs and then blood sampling.
- e Tuberculosis testing will be conducted based on clinical assessment of TB risk (symptoms/signs/known or suspected TB exposure; risk factors detailed in [Appendix 5](#)), determined by the principal investigator, and according to local regulations and/or local standard of care (Section 9.4.6). Tuberculosis testing will be performed locally using an interferon- γ release assay (IGRA; QuantiFERON®-TB Gold or T-SPOT.TB®) or a purified protein derivative (PPD) tuberculin skin test. If the PPD test is performed, patients will return 2 to 3 days afterwards to have their PPD test read. For additional details on TB testing, see Section 9.4.5.2.
- f The preferred order of completion is supine ECG prior to vital signs, blood sampling, or any other study procedures. For additional details on ECG collection, see Section 9.4.1. ECG should be performed at the ETV and Visit 802 only if there is early termination due to a cardiovascular event.
- g A Self-Harm Follow-Up Form is to be completed only during visits for which there is at least 1 discrete self-harm event identified on the Self-Harm Supplement Form (see Section 9.2.2).
- h Patients will self administer injections starting at Visit 14. Sites will train patients on how to self inject the drug at Visit 14 and will provide a log for patients to track their at home dosing.
- i The PSSI, NAPSI, and PPASI assessments are applicable only if symptoms are present at baseline.
- j These assessments should be completed before administration of IP; before the patient's clinical examination; before the patient receives any tests or results; and before the patient's health, health data, or emotions are discussed.
- k Unscheduled blood chemistry and hematology panels may be performed at the discretion of the investigator. See [Appendix 2](#), for details.

- ^l Any enrolled patient who is HBcAb+ in the originator trial will undergo monitoring of HBV DNA with HBV DNA testing (see Section 9.4.5.3). Any patient with a positive HBV DNA test at any time must be discontinued from the study and receive appropriate follow-up medical care, including consideration for antiviral therapy.
- ^m Any enrolled patient with a history of HCV infection (tested positive for HCV antibody in the originator study) who develops elevated ALT >3xULN will be tested for HCV RNA (see Section 9.4.5.4). Any patient with a positive HCV RNA test must be discontinued from the study and receive appropriate follow-up medical care, including consideration for antiviral therapy.
- ⁿ Immunogenicity samples should be collected prior to dosing on visits when mirikizumab is administered. A sample will be obtained at unscheduled visits if a patient develops an acute hypersensitivity event after administration of IP (see Section 7.8.2.1).
- ^o Sample from last visit of originator study should be used. If no sample <4 weeks old is available, then a baseline sample should be collected in this study.
- ^p Scheduled pharmacokinetic samples are taken as an aliquot from the immunogenicity sample. Unscheduled pharmacokinetic samples, obtained if a patient develops an acute hypersensitivity event after administration of IP (see Section 7.8.2.1), will be collected in a separate tube. To be performed only on women of child-bearing potential. Between visits, urine pregnancy tests are to be performed monthly at home.
- ^r If a patient discontinues IP early, the patient will complete the ETV and then enter the Post-Treatment Follow-up Period (Visit 801 and Visit 802).
- ^s Urinalysis assessed only for early termination due to an adverse event for which urinalysis is clinically indicated.

3. Introduction

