8.1. Discontinuation from Study Treatment

8.1.1. *Permanent Discontinuation from Study Treatment*

Patients for whom investigational product should be permanently discontinued, irrespective of the reason, should complete the Post-Treatment Follow-Up and then be permanently discontinued from the study. Section 8.2 provides the list of criteria for permanent discontinuation of patients from study treatment and the study.

Patients discontinuing from the investigational product prematurely for any reason should complete AE and other follow-up procedures per Section 2 (Schedule of Activities), Section 5.1.3 (Post-Treatment Follow-up Period), Section 9.2 (Adverse Events), and Section 9.4 (Safety) of this protocol.

8.1.2. *Temporary Interruption (Withholding) of Study Treatment*

Some possible reasons for temporarily withholding investigational product include, but are not limited to, the following:

- Development of:
 - Serious or opportunistic infections, as described in Section 9.2.3).
 - Hypertension (see Section 9.4.2.1).
 - Latent tuberculosis (TB) infection (LTBI) (see Section 9.4.5.2).
 - Positive hepatitis B virus (HBV) deoxyribonucleic acid (DNA) results that are below the level of quantification (see Section 9.4.5.3).
 - Hepatic event or liver test abnormality: Investigational product should be withheld and additional testing performed following consultation with the Lilly-designated medical monitor, if the results of repeat tests following elevated alanine aminotransferase (ALT), alkaline phosphatase (ALP) or total bilirubin level (TBL) include one of the following (Section 9.4.6.1):
 - $ALT \geq 3 \times$ upper limit of normal (ULN) and $TBL < 2 \times ULN$
 - $ALP \geq 2 \times ULN$ and $TBL < 2 \times ULN$
 - $TBL \geq 2 \times ULN$ without increase from baseline in ALT/aspartate aminotransferase (AST)/ALP.
- Surgery: Patients requiring surgery at any time during the study should interrupt administration of the investigational product, beginning 8 weeks before the surgery or as early as possible within 8 weeks of surgery, and resume administration of the investigational product only after complete wound healing.

Cases that may merit temporary withholding of the study treatment should be discussed with the medical monitor. The medical monitor, in consultation with the investigator, will determine when it is appropriate to recommence study treatment.

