8.2. Discontinuation from the Study

Patients should permanently discontinue the investigational product, complete the Post-Treatment Follow-up, and then permanently discontinue from the study for any of the following reasons:

- **Patient Decision**
 - The patient requests to be either discontinued from investigational product or withdrawn from the study.
- **Discontinuation due to a hepatic event or liver test abnormality.** Patients who are discontinued from investigational product due to a hepatic event or liver test abnormality should have additional hepatic safety data collected via eCRF.

Discontinuation of the investigational product for abnormal liver tests **should be** considered by the investigator when a patient meets one of the following conditions after consultation with the Lilly-designated medical monitor:

- ALT or AST >8xULN
- ALT or AST >5xULN for more than 2 weeks
- ALT or AST >3xULN and TBL >2xULN or international normalized ratio (INR) >1.5
- ALT or AST >3xULN, with the appearance of fatigue, nausea, vomiting, right upper-quadrant pain or tenderness, fever, rash, and/or eosinophilia (>5%)
- ALP >3xULN
- ALP >2.5xULN and TBL >2xULN

- ALP >2.5xULN, with the appearance of fatigue, nausea, vomiting, right quadrant pain or tenderness, fever, rash, and/or eosinophilia (>5%)
- In addition, patients who meet any one of the following criteria should be discontinued from the investigational product, enter the Post-Treatment Follow-Up Period, and discontinue from the study:
 - Total white blood cell count <2000 cells/ μ L (<2.00x10³/ μ L or <2.00 GI/L).
 - Lymphocyte count <500 cells/ μ L (<0.50x10³/ μ L or <0.50 GI/L).
 - Platelet count <50,000 cells/ μ L (<50x10³/ μ L or <50 GI/L).
 - Changes in blood pressure (BP) (systolic BP at \geq 160 mm Hg plus \geq 20 mm Hg increase from baseline [Week 0; Visit 2]; and/or diastolic BP at \geq 100 mm Hg plus \geq 10 mm Hg increase from baseline) that do not respond following maximal allowed intervention (further explanation in Section 9.4.2 of this protocol).
 - The patient experiences a severe AE, an SAE, or a clinically significant change in a laboratory value that, in the opinion of the investigator, merits the discontinuation of the investigational product.
 - Clinically significant systemic hypersensitivity event following administration of investigational product.
 - The patient becomes pregnant.

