 - The patient develops a malignancy (note: patients may be allowed to continue if they develop no more than 2 non-melanoma skin cancers during a 12-month period).
 - Any patient who has a change in disease phenotype at any time (for example, a change to pustular psoriasis).
 - It is recommended that the patient be assessed by an appropriately trained professional to assist in deciding whether the patient is to be discontinued from study treatment if:
 1. The patient, at any time during the study, scores a 3 for Item 12 (Thoughts of Death or Suicide) on the 16-item Quick Inventory of Depressive Symptomatology (QIDS-SR16);OR
 2. The patient develops active suicidal ideation with some intent to act with or without a specific plan (“yes” to Question 4 or 5 on the “Suicidal Ideation” portion of the Columbia-Suicide Severity Rating Scale [C-SSRS])OR

3. The patient develops suicide-related behaviors as recorded on the C-SSRS.
 - The patient develops active TB or HIV/AIDS during the study.
 - The patient becomes HBV DNA positive or hepatitis C virus (HCV) ribonucleic acid (RNA) positive. The patient should be referred to a specialist physician (see Sections 8.1.2 and 9.4.5.3 for HBV, and Section 9.4.5.4 for HCV).
- Patients will also be permanently discontinued from study drug, complete the Post-Treatment Follow-up, and then permanently discontinue from the study in the following circumstances:
 - Enrollment in any other clinical study involving an investigational product or enrollment in any other type of medical research judged not to be scientifically or medically compatible with this study
 - Participation in the study needs to be stopped for medical, safety, regulatory, or other reasons consistent with applicable laws, regulations, and Good Clinical Practice (GCP)
 - Investigator decision
 - The investigator decides that the patient should be discontinued from the study
 - If the patient, for any reason, requires treatment with another therapeutic agent that has been demonstrated to be effective for treatment of the study indication, discontinuation from the study occurs prior to introduction of the new agent

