9.4.5.3. Hepatitis B Monitoring

Any enrolled patient who tested positive for hepatitis B core antibody (HBcAb+) in the originator study will undergo periodic monitoring of HBV DNA as per the Schedule of Activities (Section 2).

In addition to the above, any enrolled patient who tested HBcAb+ in the originator study and who experiences an elevated ALT or AST level >3 xULN must undergo HBV DNA testing. If the HBV DNA test is negative, the investigator should consult with the Lilly-designated medical monitor regarding further management of the patient.

If the result of the HBV DNA test is positive but below quantification, study drug should be withheld and a repeat test done immediately. The Lilly-designated medical monitor should be contacted regarding study status of the patient. If the result of the HBV DNA test is positive and quantifiable, the patient must be discontinued from the study and should receive appropriate follow-up medical care, including consideration for antiviral therapy. A specialist physician in the care of patients with hepatitis (for example, infectious disease or hepatologist subspecialists) should be consulted, and the patient should potentially be started on antiviral therapy prior to discontinuation of any immunosuppressant therapy (including study drug). Timing of

discontinuation from the study treatment, the study, and of any immunosuppressant therapy (including study drug) needs to be based on the recommendations of the consulting specialist physician in conjunction with the investigator and medical guidelines/standard of care.

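### Schedule footnote l makes study exit mandatory for any positive HBV DNA test, while Section 9.4.5.3 makes it mandatory only for a quantifiable one

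*Protocol*

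**What the plan says.** Four places in the protocol deal with a positive HBV DNA result.

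- **Section 2, Schedule of Activities, footnote l.** After a sentence that sets up monitoring for HBcAb+ patients and cites Section 9.4.5.3, the footnote gives its own rule: "Any patient with a positive HBV DNA test at any time must be discontinued from the study and receive appropriate follow-up medical care". It has no quantification threshold.
- **Section 9.4.5.3.** There are two tiers. For the lower: "If the result of the HBV DNA test is positive but below quantification, study drug should be withheld and a repeat test done immediately", followed by "The Lilly-designated medical monitor should be contacted regarding study status of the patient". For the upper: "If the result of the HBV DNA test is positive and quantifiable, the patient must be discontinued from the study".
- **Section 8.1.2.** Under the lead-in "Some possible reasons for temporarily withholding investigational product include, but are not limited to, the following", the list includes "Positive hepatitis B virus (HBV) deoxyribonucleic acid (DNA) results that are below the level of quantification" and refers to Section 9.4.5.3.
- **Section 8.2.** Under the lead-in "patients who meet any one of the following criteria should be discontinued from the investigational product", one bullet reads "The patient becomes HBV DNA positive or hepatitis C virus (HCV) ribonucleic acid (RNA) positive". It states no threshold, but refers the reader to Sections 8.1.2 and 9.4.5.3 for HBV.

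All four are current text. The amendment (a) summary lists no change to footnote l or to Section 9.4.5.3.

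**The concern.** For a quantifiable positive result, every section leads to discontinuation. For a positive result below quantification, footnote l requires the patient to leave the study, whereas Section 9.4.5.3 requires a pause, a retest and a conversation about status. Two sites could handle the same laboratory report differently, each citing the protocol.

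The stake is an unnecessary exit that cannot be undone. Section 7.8.1 says that patients who discontinue early will not be given further mirikizumab. A patient whose repeat test would have allowed dosing to resume loses the rest of a treatment period of about four years.

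**Working it through.** **Step 1: compare the required action by result.**

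| Result | Footnote l | 9.4.5.3 | 8.1.2 | 8.2 |
|---|---|---|---|---|
| Positive, quantifiable | Exit mandatory | Exit mandatory | Not listed | Exit (worded as should) |
| Positive, below quantification | Exit mandatory | Withhold, repeat, contact medical monitor; exit possible | Possible reason for temporary withholding | No threshold; refers to 8.1.2 and 9.4.5.3 |

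Only the second row differs, and the difference is mandatory versus discretionary exit. The temporary-withholding entry in 8.1.2 and the immediate repeat test in 9.4.5.3 would serve little purpose if every positive result already required exit. The two-tier rule is therefore the likelier intention.

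**Step 2: check whether the footnote's cross-reference resolves it.** The reference to 9.4.5.3 is attached to the monitoring sentence. The discontinuation sentence that follows stands alone, with no qualifier and no reference.

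**Step 3: check hepatitis C.** Footnote m and Section 9.4.5.4 agree on exit for any positive HCV RNA result. Only the HBV half of the 8.2 bullet needs attention.

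**Step 4: size per affected patient.** Inputs from the protocol: dosing every 8 weeks from Visit 1 (Week 0) to Week 208 (Section 5.1.2), and scheduled on-treatment HBV DNA tests at Weeks 8, 24, 40, 56, 72, 88, 104, 120, 136, 152, 168, 184, 200 and 208 (Schedule of Activities).

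- Total doses: 208/8 + 1 = 27.
- Doses still to come after a test at Week w, if that visit's dose has already been given: (208 − w)/8.
- Week 8: (208 − 8)/8 = 25.
- Week 104: (208 − 104)/8 = 13.
- Week 200: (208 − 200)/8 = 1.
- Week 208: 0.

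That the result returns after the visit's dose is an assumption. If it were known before dosing, each count would rise by one (26, 14 and 2 at Weeks 8, 104 and 200).

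These counts are ceilings. They assume completion to Week 208 and ignore dropout and the possible earlier end at commercial availability. The loss under 9.4.5.3 can be 0 doses, if the repeat clears the patient and dosing resumes within the 8-week interval. It can also equal the footnote's loss, if the decision after medical-monitor contact is exit. For a Week 8 test the extra loss caused by the footnote therefore lies between 0 and 25 doses. Tests triggered by raised ALT or AST under 9.4.5.3 can fall at other times and are not counted.

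**Step 5: number of patients.** The documents give neither the number of HBcAb+ patients nor the frequency of unquantifiable positive results. No count can be derived.

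**The case against.** The strongest reply is that the governing sections already handle the case. Section 9 describes the Schedule as a list of procedures and their timing, and Section 8.1.1 names Section 8.2 as the place for permanent discontinuation criteria. The 8.2 bullet sends the reader to 8.1.2 and 9.4.5.3. Sponsor contact is called for twice: 9.4.5.3 asks for it on study status, and 8.1.2 says that cases which may merit withholding should be discussed with the medical monitor, who decides with the investigator when dosing restarts. This stands as mitigation. It does not remove the footnote's unqualified requirement, which is attached to every scheduled HBV DNA test.

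Stronger readings that a reader might infer are not supported:

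- **That a site cannot comply with both texts.** It can. A site that withholds, repeats, contacts the monitor and then discontinues the patient breaches neither.
- **That Section 8.2 contradicts 9.4.5.3.** Its lead-in says should rather than must, and its cross-references point to the two-tier rule. It is ambiguous.
- **That a viraemic patient might be kept on drug.** The footnote errs the other way and removes too many.
- **That the efficacy results are compromised.** The affected group is unquantified and may be empty, and nothing in the documents supports an effect on the primary analysis.

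**Conclusion.** The inconsistency is real and narrow. Read literally, footnote l turns a discretionary exit into a mandatory one for HBcAb+ patients with a positive HBV DNA result below quantification. The error is conservative, the number affected is unknown and possibly zero, and the medical-monitor provisions in 8.1.2 and 9.4.5.3 limit the chance of harm.

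For a patient who is affected, exit is irreversible and the dose ceilings are those worked out above. They rest on the assumed completion to Week 208 and on the result returning after dosing. The correction is worth making because the footnote states a firm stopping rule that differs from the detailed section, and aligning it costs very little.

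**What to change.** **Footnote l.** In the discontinuation sentence, make the condition a positive *and quantifiable* HBV DNA test and delete *at any time*. Keep the existing requirement for medical follow-up and consideration of antiviral therapy. Then add: *for a positive result below quantification, follow Section 9.4.5.3*. A pointer is better than restating the withhold-and-repeat steps, because it leaves one home for the rule.

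**Section 8.2.** After the HBV DNA condition insert *with a quantifiable result (below quantification: see Sections 8.1.2 and 9.4.5.3)*. Leave the HCV RNA half unchanged.

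**Cost.** One footnote sentence and one qualifier at the next protocol amendment. A short memo to sites can cover the interval. Visits, tests and analyses do not change. What to do if the repeat is again unquantifiable stays where 9.4.5.3 leaves it, with the medical monitor.
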